Title:

The Effect of Constant 5% Versus Gradient (8%, 5%, and 2%) Oxygen Concentration on Development of Human Embryos to the Blastocyst Stage: A Sibling Oocyte Study

Study Type:

Prospective, Quasi-Randomized Sibling-Split Oocyte Study

Study Site:

Department of Reproductive Medicine and Gynecological Endocrinology

University Medical Centre Maribor

Slovenia

Clinical Trial Registration Number:

NCT05898178

Document Date:

April 24, 2025

Principal Investigator:

[name] [name]

[contact]

2. Study Design and Participants

Prospective sibling-split oocyte study , conducted at the University Medical Centre Maribor and included a total of 658 cumulus–oocyte complexes (COCs) collected from 44 ICSI cycles between January 2022 and January 2023. A quasi-randomisation into control and intervention groups was performed immediately after oocyte retrieval. Embryonic outcomes between different oxygen culture conditions were compared.

Eligibility Criteria

- Inclusion: Women <35 years old, BMI 18–30 kg/m², normal uterine cavity, ≥6 MII oocytes retrieved, first or second ICSI cycle, male factor infertility (non-azoospermic), blastocyst culture, GnRH antagonist protocol.
- **Exclusion**: Endometriosis, previous ovarian surgery, endocrine/metabolic disorders, PCOS.

Ethical Approval

- Institutional Ethics Committee of the University Medical Centre Maribor (No: UKC-MB-KME-1/21)
- National Medical Ethics Committee (No: 0120-405/2021/4)

All participants provided informed consent.

3. Objectives

Primary Objective

To compare the proportion of injected MII oocytes that developed into morphologically optimal blastocysts on day 5 between the control and intervention oxygen conditions.

Secondary Objectives

- Assessment of morphokinetic parameters (timing to key developmental stages)
- Incidence of abnormal cleavage patterns
- Morphometric characteristics of blastocysts (e.g., area, TE cell count)

4. Sample Size Determination

Sample size was calculated using the Sealed Envelope online tool (accessed January 2022). Based on a baseline blastocyst formation rate of 15% and a hypothesized improvement to 25% in the intervention group, 496 embryos (248/group) were required for 80% power at α = 0.05. With a buffer for potential fertilization failures, 47 patients were targeted. Ultimately, 44 patients were enrolled, contributing 521 injected sibling MII oocytes.

5. Randomization and Blinding

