A quasi-random allocation method was used post-oocyte retrieval. Group A (control) was cultured under 5% O_2 ; Group B (intervention) under a decreasing gradient from 8% to 2% O_2 . Embryologists remained blinded through a coded system.

6. Laboratory Procedures

Sibling oocytes from each patient were divided into two groups:

- Intervention Group (8–5–2% O₂): Cultured under a dynamic oxygen gradient to mimic *in vivo* conditions. Gas levels were adjusted by stage:
 - Day 0–3: 6% CO₂, 8% O₂, and 86% N₂
 - $_{\odot}$ Day 3: Oxygen concentration was reduced to 5% (6% CO₂, 5% O₂, 89% N₂).
 - o Day 3–5: Oxygen was further reduced to 2% (6% CO_2 , 2% O_2 , 92% N_2).
- Control Group $(5\% O_2)$: Cultured under fixed conditions $(6\% CO_2, 5\% O_2)$ throughout.

Common lab procedures for both groups:

Sperm prep: Density gradient centrifugation

ICSI: Standard protocol using a Nikon Eclipse TE 2000 microscope (200x magnification).

Embryo culture: G-1 PLUS (Day 1–3) and G-2 PLUS (Day 3–5) (Vitrolife, Gothenburg, Sweden).

Monitoring: Continuous time-lapse imaging with Primo Vision system (Vitrolife, Gothenburg, Sweden).

8. Statistical Analysis Plan (SAP)

Statistical analysis was performed using SPSS (SPSS Inc., Chicago, Illinois, USA). Continuous variables were tested for normality using the Shapiro-Wilk test. Data are presented as mean \pm standard deviation (SD) for normally distributed variables or as median with interquartile range (IQR) for non-normally distributed variables. Categorical data are expressed as frequencies and percentages. Group comparisons for embryological outcomes, irregular cleavage events, and clinical outcomes were carried out using the chi-square test or Fisher's exact test, depending on the expected frequencies. Odds ratios (ORs) with 95% confidence intervals (CIs) were calculated using the Baptista-Pike method for categorical variables. Morphokinetic variables were reported as median hours post-insemination (HPI) with IQR. Differences in morphokinetic timings between oxygen groups were analyzed using a linear mixed-effects model (REML), and Šídák's correction was applied for multiple comparisons at individual time points. Morphometric measurements of blastocysts graded Gardner \geq 3 were compared using unpaired t-tests, with significance determined at p < 0.05. All statistical tests were two-sided; a p-value < 0.05 was considered statistically significant throughout the study.

10. Ethical Evaluation of the Submitted Research

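### Morphometric t-tests treat sibling blastocysts as independent in a sibling-split design, so their 5% level is not assured (secondary endpoint)

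*Combined protocol and SAP*

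**What the plan says.** Section 6 (Laboratory Procedures) sets out the design: "Sibling oocytes from each patient were divided into two groups". Section 2 requires "≥6 MII oocytes retrieved" per woman and describes oocytes "collected from 44 ICSI cycles between January 2022 and January 2023". Section 4 adds: "Ultimately, 44 patients were enrolled, contributing 521 injected sibling MII oocytes". One patient can therefore supply several blastocysts to each arm.

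Section 3 lists as a secondary objective "Morphometric characteristics of blastocysts (e.g., area, TE cell count"). Section 8 (SAP) says that these measurements, in blastocysts graded Gardner 3 or higher, "were compared using unpaired t-tests, with significance determined at p < 0.05", and closes with "All statistical tests were two-sided; a p-value < 0.05 was considered statistically significant throughout the study". No patient effect, pairing or clustered standard error is stated for morphometry.

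Just before this, the SAP says "Differences in morphokinetic timings between oxygen groups were analyzed using a linear mixed-effects model (REML"). It does not name the random effects of that model.

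**The concern.** An unpaired t-test assumes that all blastocysts are independent, both within an arm and between arms. A sibling split breaks both assumptions as soon as blastocysts from one patient resemble each other. The two breaches pull in opposite directions. Likeness across arms makes the true variance of the mean difference smaller than the t-test assumes. Extra likeness within an arm, or uneven numbers from one patient in the two arms, makes it larger.

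At stake is whether p < 0.05 for area or TE cell count means what it says. This point covers that secondary objective only.

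**Working it through.** **Inputs from the documents.** 44 patients and 521 injected oocytes, so 521/44 = 11.84 per patient and about 5.9 per patient per arm; two-sided 0.05. No sample size or power is stated for morphometry. The 496 embryos in Section 4 belong to the primary endpoint, so the figure to check is the nominal 5%.

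**Assumed, because not in the documents.** The number of Gardner 3 or higher blastocysts, how they fall across patients and arms, and two variance shares (total variance 1): *r*, shared by all blastocysts of a patient (the ICC), and *a*, shared only by blastocysts of the same patient and arm (an oxygen effect that varies by patient, or a shared culture effect).

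**Formula.** Let n_iA and n_iB be patient i's counts and N_A, N_B the arm totals. Put

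- S = 1/N_A + 1/N_B
- D = Σ(n_iA/N_A − n_iB/N_B)²
- Q = Σ[(n_iA/N_A)² + (n_iB/N_B)²]

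The true variance of the mean difference, relative to the t-test's, is about

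V = (1 − r − a) + r·D/S + a·Q/S = 1 + r(D/S − 1) + a(Q/S − 1),

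and the actual two-sided error is about 2[1 − Φ(1.96/√V)].

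Q/S cannot fall below 1, so *a* never lowers the error. The shared effect *r* lowers it when D/S < 1 and raises it when D/S > 1.

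**By hand.** Suppose every patient gives 2 blastocysts to each arm (44 × 4 = 176). Then D = 0, Q/S = 2 and V = 1 − r + a.

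- r = 0.2, a = 0: V = 0.80; 1.96/√0.80 = 2.19; error about 2.8%.
- r = 0.2, a = 0.2: V = 1.00; error 5.0%.
- r = 0.1, a = 0.2: V = 1.10; 1.96/√1.10 = 1.87; error about 6.2%.

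**Simulation with no true difference.** 4,000 trials per cell (standard error about 0.3 points near 5%), 44 patients, 521 oocytes split about 6 + 6, at most one blastocyst per oocyte. The assumed share reaching Gardner 3 or higher is 15%, 25% or 50% (about 78, 130 or 260 blastocysts). With r = a = 0 the error is 4.6-5.3% over all count patterns, which reproduces the nominal level. Otherwise, V and then t-test error:

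| Counts in a patient's two arms | r | a | 15% | 25% | 50% |
|---|---|---|---|---|---|
| Chance variation only | 0.2 | 0 | 0.97; 4.9% | 0.95; 4.2% | 0.90; 3.5% |
| Chance variation only | 0.5 | 0 | 0.92; 4.2% | 0.87; 3.4% | 0.75; 2.7% |
| Chance variation only | 0.3 | 0.1 | 1.02; 5.5% | 1.04; 5.9% | 1.10; 6.2% |
| Chance variation only | 0.1 | 0.2 | 1.13; 5.8% | 1.22; 7.3% | 1.44; 9.8% |
| Yield differs strongly by patient and arm | 0.2 | 0 | 1.13; 6.6% | 1.09; 6.6% | 1.00; 5.2% |
| Yield differs strongly by patient and arm | 0.5 | 0 | 1.33; 10.0% | 1.23; 7.9% | 1.00; 5.2% |

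The formula agrees with the simulation: V = 0.871 gives 3.6% (simulated 3.4%) and V = 1.231 gives 7.7% (simulated 7.9%).

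A further simulation, with 100 to 200 blastocysts capped by oocytes and either the mature oocytes or the retrieved complexes split between arms, gives:

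- r = 0.2 to 0.4, a = 0, similar yields in a patient's arms: about 3-5%
- r = 0.2 to 0.4, a = 0, yields differing by patient and arm: about 5-9%
- r = 0.2, a = 0.1 to 0.2: about 5-12%

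**After the fix.** A paired t-test on patient-arm means gave 4.5-6.1% in seven scenarios where the unpaired test ran from 0.7% to 12.8%. It used on average about 19 to 43 of the 44 patients.

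**The case against.** The strongest reply is that the harm may be slight. If 15-25% of oocytes yield a measurable blastocyst (78 to 130 of 521, borrowing the blastocyst formation rates in Section 4), if the retrieved complexes are split evenly, and if r = 0.2 with *a* between 0 and 0.1, simulated error is 4.3-6.2%. Larger inflation needs a sizeable patient-by-arm share or strongly unequal yields in a patient's two arms, and the documents show neither. This stands. A reader might infer that the morphometric p-values cannot be relied on in either direction; that goes too far.

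A reader might also infer that ignoring the pairing is merely conservative, or that it must inflate false positives. Neither is supported. The first needs similar counts in a patient's arms and little patient-by-arm variance; the second needs the opposite.

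The contrast with the morphokinetic analysis should not be pressed either. It shows that the SAP already uses this type of model, but not that the model contains a patient term.

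Finally, the document is dated April 2025 and describes the analysis as done. That does not remove the defect, but it rules out rewriting the sentence as if another test had been planned.

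**Conclusion.** The omission is certain from the text: an unpaired t-test with no account of patient, in a design that splits each patient's oocytes across arms. Its nominal 5% level is therefore not assured. Under the assumptions above the actual level runs from about 3% to about 12%, with several cases near 5%. Which case applies here cannot be settled from the documents.

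The point concerns a secondary endpoint. A reader might take that as clearing the primary comparison; it does not. The chi-square and Fisher tests of embryological outcomes also state no patient adjustment, and they are not assessed here.

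**What to change.** Keep the t-test sentence as the record of what was done, and add a re-analysis labelled post hoc:

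> Each morphometric variable of Gardner ≥3 blastocysts is compared with a linear mixed model (REML) with oxygen group as fixed effect and random effects for patient and patient-by-arm, with degrees of freedom equal to contributing patients minus 1 (or Satterthwaite); the mean difference with 95% CI is reported beside the t-test result, and conclusions rest on the mixed model.

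Name the degrees-of-freedom method, because the error rate shifts slightly with it. State that the patient-by-arm variance may be estimated as zero in some fits: in small checks (150 runs each, r = 0.2) this happened in 51-57% of fits when it was truly zero and 15-33% when its share was 0.1. Report D/S and Q/S, which follow from the existing counts and show how far each variance share can move the t-test.

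A paired t-test on patient-arm means is a simple valid check, but it drops patients without a blastocyst in both arms. For a 0.45 SD difference at r = 0.2, a = 0 and chance variation in counts, its simulated power at 100/150/200 blastocysts is 47/69/84%, against 61/78/91% for the mixed model and 60/78/89% for the unpaired t-test.

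The cost is one added passage and a re-run on existing data, provided that each measurement carries its patient identifier. Power gains little at low ICC and may fall slightly (61/76/88% against 62/77/89% at r = 0.1 in the same setting). Standard errors will be wider where the t-test is anti-conservative.
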